Figure 2: A) Improvement in Canadian Cardiovascular Society (CCS) class, Seattle Angina Questionnaire (SAQ) score, and 6 minute walk test (6MWT) at 4 months post CS Reducer implantation. B) Improved myocardial perfusion reserve index in a subgroup of patients. Adapted from Giannini F et al., JACC Cardiovascular Interventions ³².

More supportive data for the concept that increased CS pressure might improve microvascular function can be found in a very recent case presented by Tommaso Gori ³⁹ of a 61 year old man who presented with severe (CCS class 4) angina, non-obstructive CAD and elevated IMR. This patient was treated with Reducer implantation with consequent resolution of angina and dramatic reduction in IMR. Also, CS pressure elevation using pressure-controlled

intermittent CS occlusion (PISCO) in patients presenting with first anterior STEMI, resulted in improves microvascular function (reduction in IMR values) as well as reduction of infarct size (OxAMI-PISCO study)³³.

Safety and Procedural Success of CS Reducer System and Implantation Procedure

The safety and procedural success of CS Reducer implantation has been demonstrated in one randomized clinical trial and numerous observational studies done in Europe and Canada^{36, 37, 40, 41}. To date, no feasibility and efficacy studies have been done in the United States.

Potential complications of the procedure include dissection or perforation of the CS and device migration. However, as demonstrated in previous studies (COSIRA, n=52 and REDUCER-I, n=204) and non-published post-marketing commercial use in more than 1800 patients worldwide, no cases of mortality has been recorded and the rates of aforementioned complications, including myocardial infarction or permanent damage related to the device or procedure such as perforation, are very low (Table 1). Moreover, implantation procedure has very high success rates. The largest multicenter Italian registry reports 98.6% (n=139) procedural success with 2 patients (1.4%) failing due to unfavorable anatomy of the coronary sinus⁴¹. Summary of technical success data of CS Reducer implantation procedure from four previous studies is summarized in Table 2.

Table 1: Safety Data of CS Reducer System and Implantation Procedure³

Potential Complications (REDIFU-002 Reducer IFUCE Mark REV K)	Pre-Market Event Rate (COSIRA) N=52 n(%)	Post-Market Event Rate (REDUCER-I) N=204 n(%)	Post-Market Event Rate (Commercial Use) N=1840 n(%)

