Allergic reaction	0(0.00)	0(0.00)	0(0.00)

Arrhythmias (e.g. ventricular tachycardia (VT) or ventricular fibrillation (VF))	1(1.92)	4(1.96)	0(0.00)
Dissection (e.g. coronary sinus)	0(0.00)	4(1.96)	2(0.11)
Embolism (e.g. pulmonary or vessel)	0(0.00)	0(0.00)	0(0.00)
Conduction Disturbances	0(0.00)	0(0.00)	0(0.00)
Hypotension/hypertension	0(0.00)	0(0.00)	1(0.05)
Infection	0(0.00)	0(0.00)	0(0.00)
Access site complications	1(1.92)	1(0.49) ²	0(0.00)
Access site hematoma (not SAE)	Not reported	8(3.92)	Not reported
Access site minor bleed (not SAE)	Not reported	4(1.96)	Not reported
Ischemic events (e.g. myocardial infarction (MI) or unstable angina)	1(1.92)	0(0.00)	0(0.00)
Minor or major bleeding events (e.g. hemorrhage, cardiac tamponade, or pericardial effusion)	1(1.92)	1(0.49)	1(0.05)
Vascular event (e.g. pseudoaneurysm or thrombus)	0(0.00)	0(0.00)	0(0.00)
Perforation/rupture of coronary sinus, right atrium (RA), or internal jugular vein	0(0.00)	1(0.49)	3(0.16)
Pulmonary edema	0(0.00)	0(0.00)	0(0.00)
Reducer and/or coronary sinus occlusion (e.g. thrombus)	0(0.00)	0(0.00)	0(0.00)
Reducer fracture	0(0.00)	0(0.00)	0(0.00)
Reducer malposition, migration or embolization	2(3.85)	2(0.98)	10(0.54)
Respiratory failure	0(0.00)	0(0.00)	0(0.00)
Spasm of CS or jugular vein	0(0.00)	0(0.00)	0(0.00)
Cardiac valve injury (tricuspid)	0(0.00)	0(0.00)	0(0.00)
Myocardial damage	0(0.00)	0(0.00)	0(0.00)
Pyrogenic immunological or toxicological reaction	0(0.00)	0(0.00)	0(0.00)
Angina	0(0.00)	3(1.47)	0(0.00)
Chest pain ¹	1(1.92)	1(0.49)	0(0.00)

Minor neurologic event, including dysphagia, blurred vision, or TIA	0(0.00)	3(1.47)	0(0.00)
---	---------	---------	---------

¹*Chest pain has previously been categorized as angina and is therefore not currently included as an independent complication in the IFU*

²*Access Site Complications: one (1) access site complication due to device retrieval via the femoral vein*

³*Source: 022-CLN-012-2019 Rev A*

Table 2: Technical Success of CS Reducer Implantation Procedure

Study	N	Technical Success % (n)
COSIRA Treatment Arm	52	96.2 (50/52) ¹
FIM	15	93.3 (14/15) ²
REDUCER-I Overall	211	96.6 (204/211) ³
REDUCER-I Arm 1	161	95.6 (154/161) ³

¹ *Two subjects were not implanted – one due to inability to cannulate the CS and one due to inability to advance the guide catheter in the CS to the intended implant location*

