² *One subject experienced a migration post-implantation. The Reducer was noted to have moved during insertion but was inflated. As a result, the position of the deployed Reducer device was more proximal than desired. The dislodged Reducer then migrated and a 2nd Reducer was implanted without complications*

³ *Seven subjects were not implanted – 2 for CS dissection, 2 for tortuous anatomy, 1 for CS too small, 1 for inability to advance the guiding catheter, and 1 for movement of the Reducer while retracting the guidewire*

Accordingly, in this Phase-1 study we aim to evaluate the feasibility of CS Reducer implantation and its efficacy on invasively assessed microvascular function in ANOCA patients with CMD.

4- Study Hypothesis

In patients with ANOCA and invasive evidence of CMD, CS Reducer implantation is safe and will improve microvascular function as measured by CFR and HMR.

5- Aims

- 5.1 To evaluate the potential efficacy of CS Reducer implantation in ANOCA patients with CMD on microvascular function using invasive CFR and HMR assessments
- 5.2 To evaluate the potential efficacy of CS Reducer implantation in ANOCA patients with CMD on angina severity and frequency as assessed by CCS angina class and short-acting nitrates use, ischemia and exercise capacity as assessed by exercise bike echocardiographic stress test (EBEST), and quality of life as assessed by SAQ score.
- 5.3 To evaluate the potential efficacy of CS Reducer on left ventricular diastolic function and filling pressures as assessed by transthoracic echocardiographic parameters at peak exercise
- 5.4 To confirm the safety and feasibility of CS Reducer implantation patients with ANOCA and invasively documented CMD.
- 5.5 A successful demonstration in the proposed trial that CS Reducer implantation can be beneficial to patients with CMD will significantly advance the field of research aimed at FDA approval of the CS Reducer for treatment of ANOCA patients with CMD and opening the door to commercialization of CS Reducer for treatment of CMD, which is a critical unmet clinical need. If successful, the next stage of investigation will be the conduct of one or more pivotal registration studies to support FDA approval, and the proposed trial will provide information necessary to design these studies.

6- Study design

6.1 General Study Design:

- Prospective, single center, open label, single arm, clinical trial
- Number of participants: 30 subjects
- Duration of study: 4 months

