The first six patients will be sequentially enrolled, and subsequent enrollment will be held until one-month follow-up. Provided there are no safety concerns at this time, enrollment will continue. Staggered enrollment will help ensure that subsequent patients are not enrolled until there is adequate follow-up and safety of initial patients. The patients for this study will be recruited through the outpatient clinics in the Department of cardiology, including the Chest Pain and Coronary Physiology Clinic and the Coronary Artery Disease Clinic at Mayo Clinic. There have been over 35,000 patients seen in the Cardiovascular Division at Mayo Clinic yearly. There are over 6,000 cardiac catheterizations performed yearly in the cardiac catheterization lab. As a part of our clinical practice, patients with angina referred to the catheterization laboratory for a clinically indicated coronary angiography and found to have non-obstructive CAD are undergoing a comprehensive coronary reactivity testing including assessment of microvascular function with CFR and HMR. Typically, 8-10 patients per month undergo this comprehensive coronary physiology study. This will be mediated through referring physicians. Patients that meet inclusion and exclusion criteria will be considered for recruitment in the study.

7.4 When and How to Withdraw Subjects:

Subjects will be withdrawn from the study prior to completion of all study related procedures if 1 of 5 consecutive patients have serious adverse safety events.

7.5 Data Collection and Follow-up for Withdrawn Subjects:

Even though a subject has withdrawn from the study, it may be important to collect some follow-up or survival data on such subjects throughout the protocol defined follow-up period. Such data is important to the integrity of the final study analysis since early withdrawal could be related to the safety profile of the study device and/or implantation procedure. If a subject withdraws consent to participate in the study, for subject safety reasons, we will make attempts to obtain permission to collect follow up information whenever possible.

[figure not shown]

Figure 3: Flow chart of the study design. CAD: coronary artery disease; CMD: coronary microvascular dysfunction; CRT: coronary reactivity testing; CFR: coronary flow reserve; HMR: Hyperemic microvascular resistance; CCS: Canadian cardiovascular society; SAQ: Seattle angina questionnaire; EBEST: Exercise bike echocardiographic stress test.

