13.14 Stopping Rules

The principal investigator will review all serious adverse events and be involved in the decision to stop the study. The study will be stopped if 3/5 patients experience serious adverse events deemed secondary to the study device, including death, cardiovascular mortality, bleeding, stroke or sepsis thought to be secondary to CS Reducer implantation. Given that the CS Reducer has no FDA approved indication yet, and to ensure independent review and reporting of adverse events and determine if study stopping criteria have been met, a DSMB committee will be formed. The committee will be formed of 3 independent members: [name], an independent interventional and structural heart disease expert will be a member and chair the committee, and the remaining 2 members will be an independent cardiologist who evaluates and manages patients with coronary microvascular dysfunction at Mayo Chest Pain Clinic, and an independent Mayo Clinic statistician. These members will be named prior to initiation of the study.

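### The 3/5 stopping rule (13.14) does not define its five patients or accumulate events, is unreconciled with 7.3 and 7.4, and often stays silent at a 20% device-SAE rate

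*Combined protocol and SAP*

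**What the plan says.** Section 13.14 states: "The study will be stopped if 3/5 patients experience serious adverse events deemed secondary to the study device, including death". Bleeding, stroke and sepsis thought secondary to implantation fall under the same threshold. The section does not say whether the five are consecutive, fixed cohorts, the first five, or shorthand for 60%. The DSMB is set up for independent review and to "determine if study stopping criteria have been met, a DSMB committee will be formed"; no boundary of its own is given. Section 6.1 gives the size: "Number of participants: 30 subjects".

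Two other provisions bear on overlapping events.

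- Section 7.3: "The first six patients will be sequentially enrolled, and subsequent enrollment will be held until one-month follow-up". Then: "Provided there are no safety concerns at this time, enrollment will continue". Safety concerns are not defined, and no later hold is described.
- Section 7.4 withdraws subjects "if 1 of 5 consecutive patients have serious adverse safety events". It is not limited to device-related events. It does not say whether the affected subjects or all subjects are withdrawn, or whether the study stops.

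Three further provisions carry no number. Section 13.4 requires immediate contact with the medical monitor after a death or a device-related SAE. Section 13.13 requires reporting of a clinically important rise in serious suspected reactions. Section 13.15 calls for regular review of SAE numbers and types.

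For background rates, the safety part of Section 3 says of earlier use that "no cases of mortality has been recorded". The highest Table 1 entry not marked as a non-SAE is "Reducer malposition, migration or embolization", 2 of 52 (3.85%). Access-site hematoma is slightly higher at 3.92% but is marked as not an SAE.

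**The concern.** A rule confined to five patients forgets what happened earlier. Two device-related SAEs in each group of five never meet it, however many groups pass. Because deaths are pooled with other events, two device-related deaths among five patients do not meet it either, although Section 3 reports none in earlier use. The device is a permanent implant without an FDA-approved indication. This is the only place where the protocol commits in numbers to stopping, and no stopping probability is given for it. The DSMB is asked to apply a criterion whose denominator is undefined and which sits beside a much stricter threshold in Section 7.4.

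**Working it through.** **Inputs.** N = 30 (6.1) and the 3-of-5 threshold (13.14). The protocol gives no target event rate or operating characteristic for the rule, so there is no figure of its own to reproduce. True rates p of 5% to 40% are assumed for illustration. Events are taken as independent, at a constant rate, and known before the next patient is counted.

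**Most events that never meet 3/5, by reading**

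- Fixed blocks of five: 6 × 2 = 12.
- Any five consecutive patients (rolling): 12, by exact dynamic programming. The pattern 1,1,0,0,0 repeated six times attains it.
- Cumulative 60%: 17, since 18/30 = 60%.
- First five only: 2 + 25 = 27.
- If the 7.3 hold is read strictly (no event in the first six), the rolling maximum falls to 10.

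**How unusual 12 is.** There are C(30,12) = 86,493,225 ways to place 12 events. Fixed blocks let C(5,2)^6 = 1,000,000 through (1.2%). The rolling rule lets 2,520 through (0.003%).

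**Probability of ever firing.** For one group of five, b = P(X ≥ 3), X ~ Bin(5, p). At p = 0.20, b = 0.0579, so fixed blocks give 1 − (1 − 0.0579)^6 = 0.301. The rolling figure comes from an exact recursion on the last four outcomes.

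| True rate | Fixed blocks | Rolling five | Cumulative 60% |
|---|---|---|---|
| 5% | 0.7% | 1.7% | 0.1% |
| 10% | 5.0% | 10.7% | 0.9% |
| 20% | 30.1% | 48.8% | 6.1% |
| 30% | 65.6% | 83.1% | 18.1% |
| 40% | 89.9% | 96.9% | 37.8% |

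**Does the form of the rule cost anything?** Compare it with cumulative counts whose false stopping is similar. Each is an exact binomial test of the running count after every patient, at a constant nominal level. They are yardsticks only, not proposals.

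- Against the rolling rule: testing against 5% at nominal level 0.0038 puts the limit at 2 events for patients 1–2, 3 for 3–7, 4 for 8–13, 5 for 14–21 and 6 for 22–30. It stops 1.1% of the time at a true 5% and 11.0% at 10% (rolling: 1.7% and 10.7%), 62% at 20% (rolling 49%) and 94% at 30% (rolling 83%).
- The gain depends on the boundary's shape. Testing against 10% at nominal 0.0471 gives 1.5% at 5%, 10.7% at 10%, 57% at 20% and 91% at 30%.
- Against fixed blocks: testing against 5% at nominal 0.00116 gives 0.3% at 5%, 5.0% at 10%, 46% at 20% (blocks 30%) and 87% at 30% (blocks 66%).

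**Background rates.** Table 1 rows not marked as non-SAE sum to 7/52 = 13.5%, 20/204 = 9.8% and 17/1,840 = 0.9%. These are upper bounds on a per-patient rate, since one patient may appear in several rows and not every row need be a device-related SAE.

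**The case against.** The other side has several good points.

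- **The worst case is contrived.** A reader might infer that 12 of 30 affected patients is a realistic outcome without a stop. The calculation does not support that: random ordering lets 12 events through 0.003% (rolling) or 1.2% (blocks) of the time, and at a true 40% rate the rule fires 97% or 90% of the time. This stands. The moderate-rate probabilities carry the point.
- **The rule does work at high rates.** A reader might infer that it usually fails at any rate well above Table 1. At 30% it fires 66% or 83% of the time, and 20% is not far above the largest Table 1 column sum (13.5%, itself an upper bound). This stands as a limit on the claim.
- **Section 7.4 could supersede 3/5.** A reader might infer that the weakness remains however 7.4 is resolved. It does not: if 7.4 were a study-level stop, the first SAE would trigger it. But 7.4 speaks of withdrawing subjects and does not say that the study stops, so the conflict has to be settled.
- **Other safeguards exist.** The DSMB, the hold after six patients, medical-monitor contact and regular SAE review could all act earlier, and nothing in 13.14 forbids stopping on judgement. It would be wrong to say that oversight rests on this rule alone. None of these safeguards carries a number, though, and the hold occurs once.
- **A cumulative count may gain little, or cost pauses.** A boundary calibrated to a 5% rate, with about 4.5% false stopping there, stops 80% of the time at 20% but also about a quarter of the time (25–26%) at a true 10%. A boundary tested against 10%, with 9.7% false stopping, reaches only 54% at 20% against the rolling rule's 49%. The cost is real and the gain varies, but at closely matched false stopping the examples above still favour the cumulative count.

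**Conclusion.** The concern holds in limited form. Section 13.14 leaves the five patients undefined, keeps no cumulative count and has no separate provision for death. On the two consecutive-patient readings the rule fires 30% or 49% of the time at a true 20% device-SAE rate, when 0.20 × 30 = 6 affected patients are expected. On the 60% reading it fires 6% of the time; on the first-five reading, 5.8%. At matched false stopping, the illustrative cumulative count gains about 13 percentage points over the rolling reading at 20% (62% against 49%) and 11 at 30% (94% against 83%). The other boundary shape shown gains about 8 at each. The form of the rule therefore gives up sensitivity for little or no benefit. The figure of 12 in 30 is an exact upper limit for consecutive fives, not a forecast.

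These numbers assume independent events at a constant rate, known without delay, with 13.14 acting alone. With four months of follow-up, events may surface after later patients are implanted, which would weaken any such rule. How 13.14 relates to 7.3 and 7.4 cannot be settled from the text. This is a should-fix point.

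**What to change.** Reconcile Sections 7.3, 7.4 and 13.14 into one study-level safety rule. State which patients are counted, which events count, whether 7.4 concerns individual withdrawal or the whole study, what counts as a safety concern at the six-patient hold, and whether a device-related death is handled separately.

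Before the first implant, have the statistician already on the DSMB evaluate a boundary counted over all implant attempts, and print its stopping probabilities in 13.14 across a range of true rates beside those of any five-patient rule that is kept. The acceptable and unacceptable rates, the thresholds and the response to a death are for the DSMB and sponsor; none is proposed here.

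The cost is a reconciled paragraph and a small table. The downside, depending on the rates chosen, is a higher chance of a pause when the device is acceptable. The table would make that trade-off visible in advance.

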13.15 Medical Monitoring

It is the responsibility of the sponsor-investigator to oversee the safety of the study. This safety monitoring will include careful assessment and appropriate reporting of adverse events as noted above, as well as the construction and implementation of a site data and safety-monitoring plan (see section 17 below; Study Monitoring, Auditing, and Inspecting). Medical monitoring will include a regular assessment of the number and type of serious adverse events.

14- Data Handling and Record Keeping

The data collection tool for this study will be sponsor-investigator defined case report forms. The investigator will maintain complete and accurate study documentation in a separate file. Study documentation may include medical records, records detailing the progress of the study for each subject, signed informed consent forms, study device disposition records, correspondence with the study coordinator study monitor/sponsor, screening and consent information, severe adverse event reports, laboratory reports, subject diaries, data clarifications requested by the sponsor, and any other documentation deemed relevant and pertinent to the study and the study subjects. Subject data necessary for analysis and reporting will be entered into a validated database or data system in accordance. Clinical data management will be performed in accordance with applicable data management vendor standards and data cleaning procedures. The investigator is responsible for the procurement of data and for the quality of data recorded on the CRFs. The handling of data by the sponsor-investigator, including data quality assurance, will comply with regulatory guidelines (e.g., ICH GCP) and the standard operating procedures of the sponsor.

14.1 Confidentiality

Information about study subjects will be kept confidential and managed according to the requirements of the Health Insurance Portability and Accountability Act of 1996 (HIPAA). Those regulations require a signed subject authorization informing the subject of the following:

- What protected health information (PHI) will be collected from subjects in this study
- Who will have access to that information and why
- Who will use or disclose that information

- The rights of a research subject to revoke their authorization for use of their PHI.

In the event that a subject revokes authorization to collect or use PHI, the investigator, by regulation, retains the ability to use all information collected prior to the revocation of subject authorization. For subjects that have revoked authorization to collect or use PHI, attempts should be made to obtain permission to collect at least vital status (long term survival status that the subject is alive) at the end of their scheduled study period.

14.2 Source Documents

Source data is all information, original records of clinical findings, observations, or other activities in a clinical trial necessary for the reconstruction and evaluation of the trial. Source data are contained in source documents. Examples of these original documents, and data records include: hospital records, clinical and office charts, laboratory notes, memoranda, subjects' diaries or evaluation checklists, pharmacy dispensing records, recorded data from automated instruments, copies or transcriptions certified after verification as being accurate and complete, microfiches, photographic negatives, microfilm or magnetic media, x-rays, subject files, and records kept at the pharmacy, at the laboratories, and at medico-technical departments involved in the clinical trial.

14.3 Case Report Forms

The study case report form (CRF) is the primary data collection instrument for the study. All data requested on the CRF must be recorded. All missing data must be explained. If a space on the CRF is left blank because the procedure was not done or the question was not asked, write "N/D". If the item is not applicable to the individual case, write "N/A". All entries should be printed legibly in black ink. If any entry error has been made, to correct such an error, draw a single straight line through the incorrect entry and enter the correct data above it.

All such changes must be initialed and dated. Do not erase or use “white-out” for errors. For clarification of illegible or uncertain entries, print the clarification above the item, then initial and date it. If the reason for the correction is not clear or needs additional explanation, neatly include the details to justify the correction.

15- Data Management

